Most individuals with inflammatory myelopathy have lost normal voluntary control of lower extremity function. Functional Electrical Stimulation cycling with the RT-300 allows the equivalent of 6000 step cycles in one hour (when cycling at 50 rpm), a little over half the normal number of steps a healthy adult takes on average per day. Six lower extremity muscle groups are simultaneously stimulated with this device. It is therefore the most efficient device in delivering electrical stimulation to subjects with complete spinal cord injury and was therefore chosen for this study.

The RT-300 FES bike has been FDA-cleared for use in general rehabilitation (the device clearance number is K072398). It has been a standard rehabilitation treatment modality at our center for several years.

7. Study Statistics

- a. Primary outcome variable.

BDNF CSF level testing

BDNF levels in the CSF of the study subjects will be measured in response to FES ergometry. BDNF has been linked to improved functional outcomes following CNS injury. We therefore chose BDNF as a surrogate marker to determine FES efficacy.

- b. Secondary outcome variables.

CSF analysis

Exploratory analysis to further understand the CSF response to FES cycle ergometry. It will be aimed at examining neurotrophins and define the molecular signature of repair in the CSF of patients with spinal cord injury.

Spasticity level:

Date: May 10, 2016
Principal Investigator: [name].
Application Number: NA_00041441

FES cycle ergometer therapy is expected to improve spasticity. This will be assessed by Modified Ashworth testing.

- c. Statistical plan including sample size justification and interim data analysis.

Sample size and power:

This is a dose finding clinical trial. Because there is limited data on BDNF CSF levels, the sample size cannot be computed at this time (power analysis cannot be performed). Instead we will use an adaptive sample size re-estimation strategy. Based on *in vivo* BDNF animal data we decided an effect size of 20% to be significant⁸⁰.

After enrolling 48 subjects (12 per group) we will estimate 2 quantities: the mean BDNF CSF level per group and the within group standard deviation of BDNF levels (averaged across the 4 groups). The sample size may then be adjusted based on the estimated effect size (estimated mean per treatment group - 80% of that estimated mean) and the estimated standard deviation. If the recalculated total sample size is equal or less than 100 then the study will proceed. Otherwise the study will be terminated at that point.

The required sample size will be computed such that it provides 80% probability of correctly selecting the amount of FES that yields the highest mean BDNF given a true 20% mean difference between the highest mean and the next highest mean.

Analysis plan:

Dependent Variables: CSF BDNF concentration, Serum BDNF concentration, CSF GDNF concentration, CSF NT-3 concentration, CSF NT-4 concentration, CSF CNTF concentration, CSF NGF concentration, CSF IL-6 concentration, CSF IL17 concentration, CSF TNF α concentration, CSF IL-1 β concentration, CSF IL-23 concentration, CSF IL-12 concentration, modified Ashworth score, mood.

Independent Variables: Intervention (FES ergometry); Timing

Approach: The distributions of all outcome variables (CSF BDNF concentration, Serum BDNF concentration, CSF GDNF concentration, CSF NT-3 concentration, CSF NT-4 concentration, CSF CNTF concentration, CSF NGF concentration, CSF IL-6 concentration, CSF IL17 concentration, CSF TNF α concentration, CSF IL-1 β concentration, CSF IL-23 concentration, CSF IL-12 concentration, modified Ashworth score, mood) will be described by treatment group (mean, median, standard deviation). The group that has the highest mean change in BDNF concentration will be used for further studies (future Phase 3 clinical trial).

Exploratory analysis will be performed to compare mean values of GDNF, NT-3, NT-4, CNTF, NGF, IL-6, IL17, TNF α , IL-1 β , IL-23, IL-12 concentration among the 4 groups using analysis of variance or suitable non-parametric methods (Kruskal-Wallis Test) if the outcome appears to be non-normally distributed.

- d. Early stopping rules.

The principal investigator may discontinue the study if the interim statistical analysis as described above indicates that the number of subjects required for this trial exceeds #80.

Patients may withdraw from the study at any time for any reason. Any investigator may discontinue a patient for any of the following reasons:

- a) The subject experiences a medical emergency that necessitates discontinuation of therapy
- b) The subject experiences a serious adverse event (WHO Grade IV-V adverse events) that is judged to be likely related to the assigned treatment group or is of severity that warrants discontinuation of assigned treatment.

Date: May 10, 2016
Principal Investigator: [name].
Application Number: NA_00041441

c) For any medical reason at the discretion of the investigator.

Individual participants will be removed from the study if they experience toxicity or complications as described above.

* Subject not compliant:

- Fails to follow directions.
- Are not compliant: participants who miss more than 3 sessions of cycling for the duration of the study.
- Unwilling to perform the second lumbar puncture prior at the end of the study.
- Become pregnant.

8. Risks

a. Medical risks, listing all procedures, their major and minor risks and expected frequency.

The medical risks are defined in the section below. This allows combining the risk and risk management in the same section for each risk.

b. Steps taken to minimize the risks.

All assessments and intervention sessions will be supervised by the Principal Investigator and/or a licensed research Physical Therapist trained in the use of FES.

For all the study procedures, the risks and risk management are defined in the sections below.

Intervention Risks:

FES

The risk associated with FES is pain at the stimulation site. **To minimize the risk**, stimulation will only be done to the participant's tolerance level. There is a minimal risk of skin burn. To further minimize the risk of skin burn, only appropriate size electrodes will be used and they will be replaced as per the manufacturer's recommendations.

The safety of FES for use during pregnancy has not been established. Therefore pregnant women will not be enrolled in the study. **To minimize the risk**, any females who are of child bearing age will be asked to undergo pregnancy testing prior to the start of the study.

Assessment Risks:

Medical History

Aside from the risk associated with disclosing personnel or protected health information outside the research study and possible discomfort with being asked personal questions, there are no known risks associated with this measurement.

Physical Exam

Date: May 10, 2016
Principal Investigator: [name].
Application Number: NA_00041441

There are no known risks associated with this assessment.

Vital Signs

There are no known risks associated with this measurement.

Modified Ashworth Scale

There is a risk of eliciting spasms during the test. Subjects will feel a quick pull of the muscle, which might be painful at times. **To minimize the risk**, one of the co-investigator trained in the procedure will perform the test.

Pregnancy testing

There is the possibility of psychological stress occurring if testing shows that the subject may be pregnant. In the event that pregnancy test results are positive, this will be disclosed to the subject. **To minimize the risks**, if the subject is uncomfortable with this arrangement, her consent to participate in this study is not recommended.

Mood assessment

Aside from the risk associated with disclosing personnel or protected health information outside the research study, there are no known risks associated with this assessment. HealthCentral, that runs the Mood24/7 website tool that has been licensed from Johns Hopkins, secures the confidentiality and privacy of patient data using industry best practices including documented standards and procedures for protecting sensitive data, encryption of data within the Mood24/7 database and tool interface, locking down all servers and network infrastructure supporting Mood24/7, limiting access to patient data to only employees that have a need, and special training for employees covering their responsibilities as far as protecting the confidentiality of sensitive data. The study team will only check on the data at the end of the collection period and not during the collection. [name] serves as the mental health consultant in this study. If a subject were to express depressive symptoms during the study, we will refer the subject to [name].

Concomitant Medications

Aside from the risk associated with disclosing personnel or protected health information outside the research study, there are no known risks associated with this measurement.

FES Trial

The risk associated with FES is pain at the stimulation site. **To minimize the risk**, stimulation will only be done to the participant's tolerance level. There is a minimal risk of skin burn. To further minimize the risk of skin burn, only appropriate size electrodes will be used and they will be replaced as per the manufacturer's recommendations.

Lumbar Puncture

The risks of a lumbar puncture are rare and include back pain, leg pain, headache, bleeding, infection, paralysis, brainstem herniation and death. About 10% of people develop a headache after a lumbar puncture. This headache may require prolonged bed rest and in some cases a blood patch in the area where the lumbar puncture was done. **To minimize the risk**, lumbar punctures will be done only in approved outpatient facilities by a certified neurologist with experience at performing this procedure.

Blood draw

Date: May 10, 2016
Principal Investigator: [name].
Application Number: NA_00041441

There risks of drawing blood include discomfort, bleeding or bruising where the needle enters the body, and in rare cases, fainting or infection. **To minimize the risks,** a trained nurse will draw the blood.

Other Risks:

Time Commitment

The time commitment for the treatment over the 3 weeks may be inconvenient. **To minimize the risks:** 1] The subject should contact the study coordinator if having problems scheduling the visits; 2] If we feel that the subject can not commit the time and effort, he/she will be excluded from the study; 3] The visits may cause moderate social, school and work disruption. The start of the study will be scheduled to lessen the disruption.

- c. Plan for reporting unanticipated problems or study deviations.

Data and Safety Monitoring Plan:

The data and safety monitoring plan has two components: internal monitoring by the PI, and periodic monitoring by the Johns Hopkins Medical Institutional Review Board.

Internal monitoring: This will be conducted under the supervision of the PI. The PI will work very closely with the study team evaluating every step of the study milestones. The PI will also oversee the review of the patient history as also the thoroughness of the completed case report forms in conjunction with all study measures. The PI will also supervise the quality of the data entry and data quality. This will ensure continuous close monitoring for safety assessments and study measurement outcomes. The PI will report unanticipated problems or study deviations in writing to the KKI Office of Research Administration and JHM-IRB.

Institutional Review Board: In the event of any serious adverse event, the IRB will be notified and all further enrollment will be temporarily halted. Any medical questions should be directed to the PI. In the event of any injury, the services at any of the Johns Hopkins Hospital will be available to the subject. However, the subject will be responsible for the payment of any treatment or hospitalization required as a result of being injured while in the study. By signing the consent form, the subject does not waive any of the legal rights which he/she otherwise would have as a subject in a research study.

- d. Legal risks such as the risks that would be associated with breach of confidentiality.

There are minimal legal risks associated with breach of confidentiality for this study. To minimize the risk of breach of confidentiality, access to participant/study data will be limited to study team members only. All study data will be stored in a departmental locked cabinet and secure database program.

- e. Financial risks to the participants.

There will be no financial risks to the subject. Any complications that arise from the treatment will be billed to the patients insurance. If the study participant has health insurance, the costs for any treatment or hospital care received as the result of a study-related injury will be billed to their health insurer. Any costs

Date: May 10, 2016
Principal Investigator: [name].
Application Number: NA_00041441

that are not paid for by the health insurer will be billed to the patient. If the study participant does not have health insurance, he or she will be billed for the costs of any treatment or hospital care received as the result of a study-related injury.

Subjects will be responsible for the cost of travel to and from the Institute, as well as any food/meals purchased throughout the day while engaged in study procedures. Valet parking is available at no cost.

9. Benefits

- a. Description of the probable benefits for the participant and for society.

Potential benefits of the proposed research to the subjects and others:

Functional electrical stimulation has been shown to increase muscle mass^{1,2}, improve bone density³, enhance cardiovascular function⁴, improve bowel function⁵, decrease spasticity⁶ and reduce bladder infection rate⁷. There has been no formal evaluation of its efficacy in restoring function following traumatic and non-traumatic spinal cord injury. A surrogate marker for FES ergometry efficacy is the CSF level of BDNF.

In addition this study will help answer the question whether the inflammatory environment changes in response to FES and whether plasma and CSF BDNF levels correlate. If that were the case then future studies might be carried out using blood instead of CSF analysis which would be a less invasive approach than proposed in this trial.

The information from this trial will benefit society as whole and future patients with inflammatory myelopathies. This study is likely to increase scientific knowledge about the use of FES ergometry, inflammatory myelopathies, and in rehabilitation medicine in general. We will also understand more clearly from a molecular level the changes that take place regarding growth factors in the CSF following FES cycle therapy. If this therapy is able to improve functional recovery from inflammatory myelopathies it will not only be of clinical importance but also provide economical benefits in terms of better quality of life and function and lower societal costs.

Importance of the knowledge to be gained:

The efficacy of FES ergometry in restoration of function following inflammatory myelopathy has not been formally studied. If FES ergometry is found to be effective in inflammatory myelopathy, it may open a new window of hope for patients with other CNS injuries and propose a mechanism for recovery. There are risks associated with this trial however, the potential of the knowledge to be gained from the study, outweigh the risks.

10. Payment and Remuneration

- a. Detail compensation for participants including possible total compensation, proposed bonus, and any proposed reductions or penalties for not completing the protocol.

There will be no penalties for not completing the protocol. No monetary compensation will be provided.

11. Costs

Date: May 10, 2016

Principal Investigator: [name].

Application Number: NA_00041441

- a. Detail costs of study procedure(s) or drug (s) or substance(s) to participants and identify who will pay for them.

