Noninfectious inflammatory myelopathies were previously often categorized as idiopathic transverse myelitis, but advances in neuroimaging and neuroimmunology have allowed more specific diagnoses, such as multiple sclerosis (MS) and neuromyelitis optica (NMO). With the exception of relapsing remitting multiple sclerosis (RRMS) there are no existing therapies that alter the course of these diseases. People with these disorders inexorably accumulate disability. In virtually every person with secondary progressive MS (SPMS) ambulation will be significantly affected leading to use of canes, walkers, and then wheelchairs. Functional electrical stimulation (FES) cycling is a method of applying low level electrical currents to the leg and buttock muscles to cause the weakened or paralyzed muscles to contract and produce a cycling motion of the legs. It has been used most in rehabilitation of patients with traumatic spinal cord injuries (SCI). Over the recent years FES cycling has become an increasingly important modality in rehabilitation of patients with paralysis. It has been shown to have multiple primary medical benefits including: increased muscle mass^{1,2}, improvements in bone density³, enhanced cardiovascular function⁴, improved bowel function⁵, decreased spasticity⁶ and reductions in bladder infection rate⁷. More importantly it has been shown to improve recovery from SCI. In a recent pilot trial [IRB protocol NA_00015238] with MS patients at our center we showed improvements on a broad array of functional and neurologic outcome measures including gait, upper extremity dexterity, and quality of life. Further, analysis of cerebrospinal fluid before FES and 3 months after initiating FES cycling revealed an enhanced neural repair program and a reduced inflammatory environment within the CNS. **One of the most important questions unanswered in regards to this technology is: How much FES is required to result in the most optimal recovery?** We currently use an experience based approach (3 to 5 FES cycling sessions per week, 1 hour each). From extensive clinical experience in our center, we suspect that the more FES is applied the better recovery is. In order to find the optimal dose of FES we identified a biomarker that can be measured in the spinal fluid of individuals receiving FES. **Brain derived neurotrophic factor (BDNF) levels correlate closely with functional recovery^{8,9}.** Voluntary exercise induces a BDNF-mediated mechanism and promotes neural plasticity in the CNS. **Currently, there are no controlled clinical trial data available on the effect of FES ergometry on neurotrophin release and functional recovery following neurological injury.** Our center specializes in chronic rehabilitation of patients with paralysis. In our clinical experience electrical stimulation leads to accelerated recovery of neurological function compared to traditional rehabilitation¹⁰. We speculate that this is in part due to local neurotrophin release resulting in neuroprotection and repair. It is unclear what the optimal "dose" of FES is, i.e., what dose is required for maximal recovery of function. **Here we propose to measure CSF BDNF concentrations in response to FES ergometry in patients with inflammatory myelopathies. In addition we will measure markers of inflammation in response to FES.** These data will be crucial for the design of a phase 3 clinical trial evaluating the efficacy of FES in patients with inflammatory myelopathies.

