
Date: May 10, 2016

Principal Investigator: [name].

Application Number: NA_00041441

2. Objectives (include all primary and secondary objectives)

Primary Objective: To determine which FES ergometry dosing regimen results in the most significant increase in CSF BDNF levels in subjects with inflammatory myelopathy. We will test the hypothesis that 5 FES cycling sessions per week result in greater increase in CSF BDNF concentrations as compared to 1 or 3 sessions and passive cycling.

- a. We will measure CSF concentrations of BDNF in response to FES ergometry (**primary outcome**).
- b. We will investigate whether there is a correlation between plasma and CSF BDNF concentrations.

Secondary Objective: To quantify changes in the CNS inflammatory environment in response to FES ergometry in subjects with inflammatory myelopathy. We will test the hypothesis that concentrations of IL-6, IL17, TNF α , IL-1 β , IL-23, and IL-12 change in response to FES ergometry.

- a. We will measure CSF concentrations of IL-6, IL17, TNF α , IL-1 β , IL-23, and IL-12 in response to FES ergometry.

3. Background (briefly describe pre-clinical and clinical data, current experience with procedures, drug or device, and any other relevant information to justify the research)

Multiple sclerosis (MS) is an inflammatory demyelinating disease of the central nervous system (CNS) of unknown etiology. It is the most common non-traumatic cause of neurologic disability in young adults and affects between 250,000 and 400,000 persons in the United States^{11;12}. The disease usually manifests in the third to fourth decade of life and affects woman two to three times more commonly than men. In about 85% of patients, the course of disease starts with a period of unpredictable relapses and remissions (called relapsing remitting MS, or RRMS). After some number of years the majority of those patients will enter a phase of the disease where they develop slowly progressive disability (called secondary progressive MS, or SPMS). In another 15% of patients the disease onset is not marked by relapses, but rather by an insidiously progressive accumulation of disability. This subtype is called primary progressive MS (PPMS). Most treatments are only effective in RRMS.

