pathway⁶³. The MAP-K cascade facilitates the phosphorylation of CREB and synapsin-I^{64,65}. Synapsin-I is involved in synaptic vesicle clustering and release while CREB plays a role in long term plasticity and memory⁶⁶⁻⁶⁸. Phosphorylation of CREB is involved in activation of its target genes including BDNF⁶⁹.

In paralyzed muscle groups, substitution for voluntary contractions with electrical stimulation may allow for activity and sensory feedback in which both have shown to enhance natural levels of BDNF. BDNF mRNA levels increase by greater than 10-fold within 3 h after stimulation with the non-NMDA receptor agonist, kainite⁷⁰. Chronic exercise can increase the expression of genes that encode several brain neurotrophins such as BDNF, nerve growth factor, and galanin. Voluntary exercise induces a BDNF and NT-3-mediated mechanism and promotes plasticity. Exercise induced up-regulation of BDNF has been shown to enhance recovery after traumatic brain injury⁹. In a model of traumatic SCI in rats, Coumans and colleagues demonstrated that axonal growth back into the spinal cord below the lesion was seen only in the presence of BDNF (infusion rate: 0.001mg/h x 14 days) or NT-3 (infusion rate: 0.0005mg/h x 14 days). Furthermore, the restoration of anatomical connections across the injury site was associated with recovery of function with animals exhibiting plantar foot placement and weight-supported stepping⁸.

There is experimental evidence that BDNF can cross the blood–brain barrier⁷¹. According to these results, BDNF changes within the CNS and CSF might be paralleled by changes of BDNF serum levels. In a trial comparing 64 patient’s CSF and plasma BDNF levels Laske et al failed to show a correlation between BDNF levels in these compartments⁷².

Reports about BDNF CSF concentrations vary widely. Reported concentrations are ranging from 6.16 ± 1.07 pg/ml⁷³ to 242 ± 37 pg/ml⁷⁴ to 21.3 ng/ml⁷² in adults. In children concentrations were reported $\sim 10 \pm 1$ pg/ml⁷⁵.

In neurological disease and injury, BDNF concentrations are generally higher. For example, there was an almost 4 fold increase reported in patients with Parkinson’s disease as compared to controls⁷³. Two hours following traumatic brain injury in children there was a 2.5 fold increase of CSF BDNF levels⁷⁵.

In the normal CNS, neurons have a major role in the synthesis of BDNF, while in the injured CNS, glial (microglial) cells produce BDNF⁷⁶.

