The discrepancies of the different BDNF levels might be explained by the difference of assays used. BDNF assays are now commercially available (RayBiotech, Norcross GA, USA). With this assay the minimum detectable dose of BDNF is typically less than 0.3 ng/ml without cross reactivity to other cytokines (Reproducibility - Intra-Assay: CV<10%, Inter-Assay: CV<12%).

4. Study Procedures

Study Design:

Phase 2 trial.

This selection study will be performed as a randomized, parallel Group Trial to determine the amount of FES ergometry required to achieve maximal CSF BDNF levels in individuals with inflammatory myelopathy.

Subjects will be randomized into 4 groups (FES1: 1 session of FES ergometry per week, FES3:3 sessions of FES ergometry per week, FES5: 5 sessions of FES ergometry per week, and Passive: 3 sessions of passive cycling per week). Session duration is 60 minutes. After obtaining a detailed physical and spasticity testing, baseline serum and CSF BDNF levels will be measured. The subjects will then receive

FES ergometry or passive cycling according to their group assignment for 3 weeks. At that time the subjects will return for a physical exam, spasticity testing, and repeat serum and CSF BDNF level testing. The primary investigator will be blinded to the results. The Study Time Line is found in Figure 1.

[figure not shown]

Figure 1: Study Time Line

Study Treatments

All activities will be conducted at INI and are supervised by a licensed physical therapist. This includes all cycling activities; all study procedures, the screening and final visits. Urine (for rapid urine pregnancy testing) will be sent to the Johns Hopkins Medicine (JHM) Pathology lab.

Functional Electrical Stimulation Ergometry

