This study is a rater-blinded randomized trial. Study physicians and research staff who perform study measurements on participants will be blinded from the intervention the study participants receive. Because of the nature of the interventions, study participant cannot be blinded to the treatment they will receive.

Justification why participants will not receive routine care or will have current therapy stopped:

All participants will receive routine care for treatment of paralysis. Participants will not be asked to stop their current medications or therapy. All subjects will continue to consistently perform their usual (“baseline”) amount of physical activity throughout the study, including home exercise stretching program, cardiovascular conditioning, etc. “Baseline” activity is defined as amount of physical activity performed for at least 1 month prior to enrollment. Routine care will not be interrupted.

Justification for inclusion of a placebo or non-treatment group:

Passive ergometry is chosen as one control to determine whether it is the active neuromuscular conduction triggered by FES that leads to alteration in CSF neurotrophin levels or whether any range of motion is sufficient. Physiological effects of FES ergometry require treatment for several months¹⁰. Our proposed

Date: May 10, 2016
Principal Investigator: [name].
Application Number: NA_00041441

study is short (3 weeks). Although we expect a short term increase in neurotrophin levels, we do not expect any functional differences between the active and passive ergometry groups.

Definition of treatment failure or participant removal criteria:

Subjects may withdraw from the study at any time for any reason.

The subject may be removed from the study for any of the following reasons:

- a) The subject experiences a medical emergency that necessitates discontinuation of therapy
- b) The subject experiences a serious adverse event that is judged to be likely related to the assigned treatment group or is of severity that warrants discontinuation of assigned treatment.
- c) For any medical reason at the discretion of the investigator.
- d) Subject is not compliant: participants who miss more than 3 sessions of cycling for the duration of the study.
- e) Subject becomes pregnant.

Description of what happens to participants receiving therapy when study ends or if a participant's participation if the study ends prematurely:

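### The primary objective promises a test that FES5 raises CSF BDNF more than FES1, FES3 and Passive, but the analysis plan pre-specifies no between-group test, contrast or interval for CSF BDNF

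*Combined protocol and SAP*

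**What the plan says.** **Objective.** The Primary Objective in section 2 has two sentences. The first is a selection aim: "To determine which FES ergometry dosing regimen results in the most significant increase in CSF BDNF levels". The second is a directional hypothesis with three comparators: "We will test the hypothesis that 5 FES cycling sessions per week result in greater increase in CSF BDNF concentrations as compared to" one or three sessions and passive cycling.

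**Design.** Section 4, Study Design: "This selection study will be performed as a randomized, parallel Group Trial to determine the amount of FES ergometry required". The four arms are FES1, FES3, FES5 and Passive. The section 4 justification for a placebo or non-treatment group says: "Passive ergometry is chosen as one control to determine whether it is the active neuromuscular conduction triggered by FES" that changes CSF neurotrophins, or whether movement alone is enough.

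**Sample size.** Section 7.c: "Because there is limited data on BDNF CSF levels, the sample size cannot be computed at this time". After 48 subjects (12 per group), the size is recalculated to give 80% probability of correctly selecting the best amount of FES, when the best mean exceeds the next by 20%.

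**Analysis.** Section 7.c lists CSF BDNF first among the dependent variables, with intervention and timing as independent variables. The outcomes "will be described by treatment group (mean, median, standard deviation"), and the group with the largest mean change in BDNF goes forward. The only between-group tests, ANOVA or Kruskal-Wallis across the four groups, are exploratory. They cover the other neurotrophins and the cytokines, not BDNF.

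**The concern.** The primary outcome carries the only hypothesis about the FES dose, yet it has no contrast, interval, significance level or multiplicity rule. The exploratory markers do get a test. Followed as written, the trial ends with a chosen group and no pre-specified answer to two questions that it sets itself: whether FES5 exceeds the other three arms, and whether stimulation adds anything to passive movement.

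The second matters for what comes next. The opening summary says: "These data will be crucial for the design of a phase 3 clinical trial evaluating the efficacy of FES". If the chosen regimen is carried into that trial, its top rank may be taken as evidence of an effect over Passive, which a ranking cannot supply.

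A lesser matter is that no sentence says whether Passive is itself a candidate for selection. The number of candidates enters the sample-size recalculation.

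**Working it through.** **No figure to reproduce.** The plan states no final size, significance level, standard deviation or power for CSF BDNF. The gap itself is read from the text; the arithmetic shows what the selection rule can and cannot do, and what a test would cost.

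**1. The rule under no difference.** With equal true means and equal arms, each candidate is equally likely to rank first. FES5 is named with probability 1/4 = 25% (four candidates) or 1/3 = 33% (FES arms only). This holds for any pick-the-winner rule.

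**2. Sizing for 80% correct selection.** Inputs from section 7.c: difference = mean − 80% of mean = 0.20 × mean; target 80%. Assumed: normal data, equal arms, the other arms tied at 80% of the best, and SD = CV × mean. With k candidates, the probability of correct selection is ∫ Φ(x+h)^(k−1) φ(x) dx, where h = 0.20√n/CV. Solving for 0.80:
- k = 3: h = 1.652
- k = 4: h = 1.893
- ratio of n per arm = (1.652/1.893)² = 0.76

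At an assumed CV of 0.50, n = (h × 0.50/0.20)²:
- k = 3: 17.1, so 18 per arm (72 in four arms)
- k = 4: 22.4, so 23 per arm (92 in four arms)

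**3. Does k change stop/go?** The largest CV that stays within each limit is 0.20√n/h:

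| Limit on total | n per arm | k = 4 | k = 3 |
|---|---|---|---|
| 80 (section 7.d, discretionary) | 20 | 0.47 | 0.54 |
| 100 (section 7.c) | 25 | 0.53 | 0.61 |

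The two readings differ only between the paired values. At CV 0.55, for example, the totals are 112 and 84.

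**4. Power of the promised test at the 20% difference.** Level scale, unadjusted, two-sided 5% (the level is assumed). One comparison is a two-sample t-test with d = 0.20/CV and noncentrality d√(n/2). At CV 0.50 and n = 18, d = 0.40 and the noncentrality is 0.40 × √9 = 1.20. Winning all three was simulated with the SD pooled over four arms and the other three arms tied.

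| CV | n per arm | One comparison | All three |
|---|---|---|---|
| 0.50 | 18 (k = 3 size) | 21% | 6% |
| 0.50 | 23 (k = 4 size) | 26% | 8% |
| 0.30 | 12 | 35% | 14% |
| 0.17 | 12 | 77% | 60% |
| 0.15 | 12 | 86% | 75% |
| 0.10 | 12 | over 99% | 99% |

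The last three CVs come from the literature values in section 3 ("Reported concentrations are ranging from 6.16 ± 1.07" pg/ml and others) if the unlabelled ± figures are SDs: 1.07/6.16 = 0.17, 37/242 = 0.15 and 1/10 = 0.10. They come from other populations and assays, and the last from children, whereas this trial enrols ages 18 to 65. The documents do not settle the CV.

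**5. Change rather than level.** The hypothesis concerns the increase. For the same absolute difference, SD of change = SD × √(2(1−r)), where r is the baseline-final correlation (assumed). A baseline-adjusted model has residual SD = SD × √(1−r²). One comparison at CV 0.50 and n = 18:

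| r | Change score | Baseline-adjusted |
|---|---|---|
| 0 | 13% | 21% |
| 0.5 | 21% | 27% |
| 0.7 | 33% | 37% |

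At r = 0 the adjusted model has the level-scale SD.

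**The case against.** **A selection study needs no hypothesis test.** This is the strongest reply, and it stands as far as it goes. Section 4 declares the design, the first sentence of the objective matches it, and the 80% correct-selection criterion is pre-specified. A reader might infer that the design itself is invalid; the documents do not support that. What remains is that the second sentence promises a test, and section 4 gives Passive a question that ranking cannot answer.

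**BDNF is compared between groups.** A reader might infer that there is no between-group comparison at all. That goes too far: ranking groups on mean change is a comparison, and intervention and timing are listed as independent variables. Neither amounts to a test, contrast or interval.

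**Passive is plainly a control.** Most of the text points to FES arms only: the first sentence of the objective, the Study Design, the control rationale and the sample-size criterion. Only the selection rule, which speaks of the group without restriction, reads as all four. A reader might infer a contradiction, or that eligibility will decide whether the trial continues. It is an ambiguity. Its effect on stop/go is confined to the narrow CV bands above and vanishes if the literature ± values are SDs, since the formula then needs at most 3 per arm under either k.

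**The FES-versus-Passive estimate is not a listed objective.** True as a separate item. But Passive is one of the three comparators in the hypothesis, and the control rationale asks this question.

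**The team could compute it later.** Paired samples are planned, so the study team could derive the SD of change. That does not make the analysis pre-specified.

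**Conclusion.** The concern holds in this form: a stated primary hypothesis has no analysis behind it, and the selection rule cannot stand in for one. This rests on the text and needs no assumed figure. Being selected would not show that FES5, or any FES arm, exceeds Passive.

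The eligibility of Passive is a minor clarification, worth a factor of about 0.76 in n per arm.

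A reader might also infer that a formal test would be hopeless here. That does not follow. The low figures (about 21% for one comparison and 6% for all three) rest on an assumed CV of 0.50, the level scale and 18 per arm, which is the three-candidate size. If the literature ± values are SDs, 12 per arm would give from 77% to over 99% for one comparison. Nor does a claim that FES5 beats all three require a multiplicity adjustment: every contrast must succeed, so testing each at the unadjusted level does not inflate the type I error.

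**What to change.** 1. Choose one of two routes. Either reword the second sentence of the primary objective as a selection aim, or pre-specify the FES5 contrasts with FES1, FES3 and Passive from one baseline-adjusted CSF BDNF model, with level and sidedness. If the claim is that FES5 beats all three, test each contrast unadjusted. Adjust for multiplicity (Dunnett is one option) only if each contrast is to be claimed separately.
2. On either route, pre-specify an FES-versus-Passive estimate with a confidence interval, including FES3 versus Passive, where session numbers are equal. State that being selected does not by itself show superiority to Passive.
3. As a clarification, state whether Passive can be selected, and use the matching number of candidate arms in the sample-size recalculation.

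The cost is wording plus one model on data already planned, with no added visits or samples. The drawback is that the contrasts may be imprecise. At CV 0.50 and 18 per arm, the 95% half-width of a change-score contrast (SD pooled over four arms) is about 47%, 33% or 26% of the mean level at r = 0, 0.5 or 0.7. Rewording avoids claiming a test but still leaves the Passive comparison to be estimated.
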